16.8. Optional Laboratory Assessments

Optional laboratory assessment consisting of DNA testing with full genome sequence data may be analyzed to evaluate genetic risk factors in the hemophilia A patient population. The analysis, however, will be in a separate report and will not be included as part of any CSR or interim CSR of 8HA01EXT.

16.9. Interim Analyses

Interim analyses will be conducted during the study, as needed. Analyses will be descriptive in nature. No formal comparisons are planned and no hypotheses will be formally tested.

Due to the open-label nature of this study, personnel involved in conducting the interim analyses will have access to treatment assignments.

16.10. Sample Size Considerations

This is an extension study. The sample size is based on the planned sample sizes of Studies 997HA301 (N=144) and 8HA02PED (N=50), and may be increased based upon subject participation in other rFVIII Fc studies or upon enrollment being greater than expected in studies 997HA301 and/or 8HA02PED.

CONFIDENTIAL

The information contained herein may not be used, disclosed, or published without the written consent of Biogen Idec MA Inc.

17. ETHICAL REQUIREMENTS

The Sponsor and the Investigator must comply with all instructions, regulations, and agreements in this protocol and applicable International Conference on Harmonisation (ICH) and Good Clinical Practice (GCP) guidelines and conduct the study according to local regulations.

17.1. Declaration of Helsinki

The Investigator and Sponsor must adhere to the principles set forth by the Declaration of Helsinki dated October 2008.

17.2. Ethics Committee

The Investigator must obtain ethics committee approval of the protocol, ICF, and other required study documents prior to starting the study.

If the Investigator makes any changes to the ICF, the Sponsor must approve the changes before the ICF is submitted to the ethics committee. A copy of the approved ICF must be provided to the Sponsor. After approval, the ICF must not be altered without the agreement of the relevant ethics committee and the Sponsor.

It is the responsibility of the Principal Investigator(s) to ensure that all aspects of institutional review are conducted in accordance with current governmental regulations.

The Sponsor must receive a letter documenting ethics committee approval, which specifically identifies the protocol, protocol number, and ICF, prior to the initiation of the study. Protocol amendments will be subject to the same requirements as the original protocol.

A progress report must be submitted to the ethics committee at required intervals and not less than annually.

At the completion or termination of the study, the investigational site must submit a close-out letter to the ethics committee and the Sponsor.

17.3. Subject Information and Consent

Prior to performing any study-related activities under this protocol, including screening tests and assessments, written informed consent with the approved ICF must be obtained from the subject or subject's legally authorized representative, as applicable, in accordance with local practice and regulations. Written informed consent must be obtained from all subjects participating in a clinical study conducted by the Sponsor.

The background of the proposed study, the procedures, the benefits and risks of the study, and that study participation is voluntary for the subject must be explained to the subject. The subject must be given sufficient time to consider whether to participate in the study.

A copy of the ICF, signed and dated by the subject, must be given to the subject. Confirmation of a subject's informed consent must also be documented in the subject's medical record prior to any testing under this protocol, including screening tests and assessments.

CONFIDENTIAL

The information contained herein may not be used, disclosed, or published without the written consent of
Biogen Idec MA Inc.

Each consent form should contain an authorization allowing the Principal Investigator(s) and the Sponsor to use and disclose PHI (i.e., subject-identifiable health information) in compliance with local law.

The signed consent form will be retained with the study records.

For subjects who are under 18 years of age (or legally a minor per local regulations), or who are otherwise unable to provide written informed consent, a parental/guardian consent will be obtained, the contents of which will be identical to that of the standard adult consent. Written subject assent will also be obtained from those subjects who are able to read and understand the assent form, a brief summary of the study process, benefits, and risks.

17.4. Subject Data Protection

Prior to any testing under this protocol, including screening tests and assessments, candidates must also provide all authorizations required by local law (e.g., PHI authorization in North America).

The subject will not be identified by name in the eCRF or in any study report, and these reports will be used for research purposes only. The Sponsor, its partner(s) and designee(s), ethics committees, and various government health agencies may inspect the records of this study. Every effort will be made to keep the subject's personal medical data confidential.

17.5. Compensation for Injury

The Sponsor maintains appropriate insurance coverage for clinical trials and will follow applicable local compensation laws.

17.6. Conflict of Interest

The Investigators should address any potential conflicts of interest (e.g., financial interest in the Sponsor) with the subject before the subject makes a decision to participate in the study.

17.7. Registration of Study and Disclosure of Study Results

The Sponsor will register the study and post study results regardless of outcome on a publicly accessible website in accordance with the applicable laws and regulations.

CONFIDENTIAL

The information contained herein may not be used, disclosed, or published without the written consent of Biogen Idec MA Inc.

18. ADMINISTRATIVE PROCEDURES

18.1. Study Site Initiation

The Investigator must not screen any subjects prior to completion of a study initiation visit, conducted by the Sponsor or designee. This initiation visit will include a detailed review of the protocol and study procedures.

18.2. Study Supplies

The Sponsor will supply the rFVIII Fc while subjects participate in this study (see Section 12). Since study subjects will be required to maintain accurate records of each dose of rFVIII Fc administered during the study, the Sponsor will provide personal eDiaries to the study sites for subjects to use to record study information.

18.3. Quality Assurance

During and/or after completion of the study, quality assurance officers named by the Sponsor or the regulatory authorities may wish to perform on-site audits. The Investigator will be expected to cooperate with any audit and to provide assistance and documentation (including source data) as requested.

18.4. Monitoring of the Study

The Principal Investigator(s) must permit study-related monitoring by providing direct access to source data and to the subjects' medical histories.

The Clinical Monitor(s) will visit the Investigator(s) at regular intervals during the course of the study and after the study has completed, as appropriate.

During these visits, eCRFs and supporting documentation related to the study will be reviewed and any discrepancies or omissions will be resolved.

Downloads from the subjects' eDiaries described in Section 19.1.3 will be used as source data.

The monitoring visits must be conducted according to the applicable ICH and GCP guidelines to ensure protocol adherence, quality of data, study treatment accountability, compliance with regulatory requirements, and continued adequacy of the investigational site and its facilities.

18.5. Study Funding

The Sponsor will pay the clinic or institution where the study is conducted for the costs of running the study. All financial details are provided in the separate contract(s) between the Institution/Investigator and the Sponsor.

18.6. Publications

Details are included in the clinical trial agreement for this study.

CONFIDENTIAL

The information contained herein may not be used, disclosed, or published without the written consent of Biogen Idec MA Inc.

19. FURTHER REQUIREMENTS AND GENERAL INFORMATION

19.1. External Contract Organizations

19.1.1. Contract Research Organization

A contract research organization (CRO) will be responsible for administrative aspects of the study including, but not limited to, study initiation, monitoring, and management of SAE reports and data management. Before subjects are screened at each study site, the CRO will review study responsibilities with the Investigators and other study site staff, as appropriate.

19.1.2. Interactive Voice/Web Response System

Interactive Voice and Web Response System (IXRS) will be used in this study. Before subjects are screened or enrolled, the IXRS vendor will provide each study site with appropriate training and a user manual.

19.1.3. Electronic Data Capture

Subject information will be captured and managed by study sites on eCRFs by a web-based electronic data capture (EDC) tool (eDiary) developed and supported by the EDC vendor and configured by the Sponsor.

Data entered by subjects using the eDiary will be downloaded to the database.

19.1.4. Central Laboratories for Laboratory Assessments

Central laboratories have been selected by the Sponsor to analyze all hematology, blood chemistry, inhibitor, and antibody samples collected for this study. Specifics regarding the requirements for laboratory specimen collection, handling, and analysis are provided in the study Laboratory Manuals, which are part of the Study Manual.

19.2. Changes to Final Study Protocol

All protocol amendments must be submitted to the ethics committee and Regulatory Authorities if required by local law. Protocol modifications that affect subject safety, the scope of the investigation, or the scientific quality of the study must be approved by the ethics committee before implementation of such modifications to the conduct of the study. If required by local law, such modifications must also be approved by the appropriate regulatory agency prior to implementation.

However, the Sponsor may, at any time, amend this protocol to eliminate an apparent immediate hazard to a subject. In this case, the appropriate regulatory authorities will be notified subsequent to the modification.

In the event of a protocol modification, the subject consent form may require similar modifications (see Sections [17.2](#) and [17.3](#)).

CONFIDENTIAL

The information contained herein may not be used, disclosed, or published without the written consent of Biogen Idec MA Inc.

19.3. Ethics Committee Notification of Study Completion or Termination

Where required, the Health Authorities and ethics committees must be notified of completion or termination of this study, and sent a copy of the study synopsis in accordance with necessary timelines.

19.4. Retention of Study Data

The minimum retention time for study records will meet the strictest standard applicable to that site, as dictated by any institutional requirements or local laws or regulations. Prior to proceeding with destruction of records, the Investigator must notify Biogen Idec in writing and receive written authorization from Biogen Idec to destroy study records. In addition, the Investigator must notify Biogen Idec of any changes in the archival arrangements including, but not limited to, archival at an off-site facility or transfer of ownership if the Investigator leaves the site.

19.5. Study Report Signatory

The Sponsor will designate one of the participating Study Investigators as a signatory for the study report. This determination will be made by several factors, including, but not limited to, the Investigator's experience and reputation in the studied indication, the Investigator's contribution to the study in terms of design, management, and/or subject enrollment, or by other factors determined to be relevant by the Sponsor.

The Sponsor will follow all applicable local regulations pertaining to study report signatories.

CONFIDENTIAL

The information contained herein may not be used, disclosed, or published without the written consent of Biogen Idec MA Inc.

23. APPENDIX B: HEMOPHILIA JOINT HEALTH SCORE (HJHS)

Appendix B1: Modified HJHS for Subjects Transferring from Study 997HA301

This modified HJHS is based on the scoring system used in a joint scoring reliability study in boys with hemophilia [Hilliard et al., 2006]. The modifications were done to adapt the scoring system to an adult hemophilia population and according to comments in a recent validation study by the international hemophilia prophylaxis study group [Feldman et al., 2011]. This version is for use only with subjects who were previously enrolled in study 997HA301.

Six joints (left ankle-LA, right ankle-RA, left elbow-LE, right elbow-RE, left knee-LK, right knee-RK) will be scored on a scale from 0 to 19 according to the following criteria: swelling, duration, muscle atrophy, crepitus, flexion loss, extension loss, instability, joint pain, and strength. Gait will be scored on a scale from 0 to 2 based on walking and climbing stairs. The total score will be the sum of scores from all 6 joints plus the gait score (range from 0 to 116 with 0 being normal and 116 being the most severe disease).

SCORING DETAILS

1. **Joint scoring will be done separately for the 6 joints (LA, RA, LE, RE, LK, RK) according to these categories and scales (range is 0-19 for each joint and 0-114 for all six joints):**

Swelling

0=none

1=mild

2=moderate

3= severe

Duration of swelling

0=no swelling or ≤ 6 months

1= >6 months

Muscle atrophy

0=none

1=mild

2=severe

Crepitus on motion

0=absent

CONFIDENTIAL

The information contained herein may not be used, disclosed, or published without the written consent of Biogen Idec MA Inc.

1=present

Flexion loss (includes plantarflexion of ankles)

0=none*

1= mild*

2= moderate*

3= severe*

Extension loss (includes dorsiflexion of ankles)

0= none*

1= mild*

2= moderate*

3= severe*

* Use the following as guidance for scoring flexion loss and extension loss at knees and elbows:

None: approximately 0-5 degrees

Mild: approximately 5-10 degrees

Moderate: approximately 11-20 degrees

Severe: approximately >20 degrees

Instability

0=none

1=significant pathologic joint laxity

Joint pain

0=no pain (either through range or at end range of motion)

1=present

Strength

0=normal (holds position against gravity and maximum resistance)

1=minimal decrease (holds position against gravity and moderate resistance, but not maximum resistance)

2=mild decrease (holds position against gravity or minimal resistance)

3=moderate decrease (able to move joint if gravity eliminated)

4=severe decrease (trace or no muscle contraction)

CONFIDENTIAL

The information contained herein may not be used, disclosed, or published without the written consent of Biogen Idec MA Inc.

2. Gait will be scored once (range is 0-2):

0=No difficulty with walking or climbing up/down stairs

1=No difficulty with walking, but difficulty with stairs

2=Difficulty with walking and with stairs

Total score = sum of all joint scores plus the gait score (range is 0-116)

Appendix B2. HJHS Version 2.1 for All Other Subjects

Pediatric subjects previously enrolled in study 8HA02PED or subjects from any other rFVIIIc study will continue to use HJHS Version 2.1 (Hemophilia Joint Health Score, Version 2.1, 2011).

CONFIDENTIAL

The information contained herein may not be used, disclosed, or published without the written consent of Biogen Idec MA Inc.

24. APPENDIX C: SUBJECT'S ASSESSMENT OF RESPONSE TO TREATMENT OF BLEEDING

Using the eDiary, each subject or the subject's caregiver will rate the treatment response to any bleeding episode using the following 4-point scale (excellent, good, moderate, or none). This assessment is to be made approximately 8 to 12 hours from the time the injection was given to treat the bleeding episode and prior to any additional doses of rFVIIIFc given for the same bleeding episode. In this study, a bleed will be defined as follows: a bleeding episode starts from the first sign of a bleed and ends no more than 72 hours after the last treatment for the bleed, within which any symptoms of bleeding at the same location, or injections less than or equal to 72 hours apart, are considered the same bleed. Any injection to treat the bleed, taken more than 72 hours after the preceding one, will be considered the first injection to treat a new bleed at the same location. Any bleeding at a different location is considered a separate bleed regardless of time from last injection. Response could also be assessed by the Physician for those subjects who were treated in the hospital with rFVIIIFc for major bleeds or post-surgery until discharge from the hospital.

- Excellent: Abrupt pain relief and/or improvement in signs of bleeding within approximately 8 hours after the initial injection
- Good: Definite pain relief and/or improvement in signs of bleeding within approximately 8 hours after an injection, but possibly requiring more than one injection after 24 – 48 hours for complete resolution
- Moderate: Probable or slight beneficial effect within 8 hours after the initial injection **and** requires more than one injection
- None: No improvement, or condition worsens within approximately 8 hours after the initial injection

The following evaluations will determine the level of hemostasis achieved with rFVIIIFc treatment during surgery:

- Number of injections and dose per injection required to maintain hemostasis during the surgical period
- Estimated blood loss during surgery (intra-operative period)
- Number and type of blood component transfusions required during surgery

CONFIDENTIAL

The information contained herein may not be used, disclosed, or published without the written consent of Biogen Idec MA Inc.

25. APPENDIX D: PHYSICIAN'S GLOBAL ASSESSMENT OF RESPONSE

Investigators will record assessments of each subject's response to his rFVIII Fc regimen using the following 4-point scale:

- Excellent: bleeding episodes responded to \leq the usual number of injections or \leq the usual dose of rFVIII Fc, or the rate of breakthrough bleeding during prophylaxis was \leq that usually observed.
- Effective: most bleeding episodes responded to the same number of injections and dose, but some required more injections or higher doses, or there was a minor increase in the rate of breakthrough.
- Partially Effective: bleeding episodes most often required more injections and/or higher doses than expected, or adequate breakthrough bleeding prevention during prophylaxis required more frequent injections and/or higher doses.
- Ineffective: routine failure to control hemostasis or hemostatic control require additional agents.

Investigators should consider the following, if available, when making the assessment:

- Frequency of rFVIII Fc injections
- Response to rFVIII Fc injection
- Information reported in the eDiary by the subject

CONFIDENTIAL

The information contained herein may not be used, disclosed, or published without the written consent of Biogen Idec MA Inc.

26. APPENDIX E: PHYSICIAN ASSESSMENT OF RESPONSE TO TREATMENT DURING SURGERY

The Investigator/Surgeon who completed the minor or major surgical procedures will assess the subject's response to surgery with rFVIII Fc treatment using a 4-point clinical scale. This includes observations during surgery. This assessment will be done within 24 hours after the surgery.

Excellent: intra-operative and post-operative blood loss similar to (or less than) the non-hemophilic patient.

- No extra doses of rFVIII Fc needed **AND**
- Blood component transfusions required are similar to person without hemophilia

Good: intra-operative and/or post-operative bleeding slightly increased over expectations for the non-hemophilic patient, but the difference is not clinically significant.

- Intra-operative blood loss no more than than expected for person without hemophilia **AND**
- No extra doses of rFVIII Fc needed **AND**
- Blood component transfusions required are similar to person without hemophilia

Fair: intra-operative and/or post-operative blood loss is increased over expectation for the person without hemophilia and additional treatment is needed.

- Intra-operative blood loss greater than expected for person without hemophilia **OR**
- Extra dose of rFVIII Fc needed **OR**
- Increased blood component transfusion requirement

Poor/none: significant intra-operative and/or post-operative bleeding that is substantially increased over expectations for the person without hemophilia, requires intervention, and is not explained by a surgical/medical issue other than hemophilia

- Intra-operative blood loss greater than for the person without hemophilia **OR**
- Unexpected hypotension or unexpected transfer to intensive care unit due to bleeding **OR**

Substantially increased blood component transfusion requirement

CONFIDENTIAL

The information contained herein may not be used, disclosed, or published without the written consent of Biogen Idec MA Inc.

27. APPENDIX F: PATIENT REPORTED OUTCOMES

The following QoL questionnaires will be presented under separate cover:

- Haem-A-QoL
- Haemo-QoL
- Hemo-Sat-P Patient Satisfaction Scale for parents/guardians, Version 15
- CHO-KLAT
 - Children, Version 2.0 (for children previously enrolled in study 8HA02PED who are less than 18 years of age).
 - Proxy, Version 2.0p (for parents/guardians of children who were previously enrolled in study 8HA02PED and who are less than 18 years of age)
- EQ-5D Y
- EQ-5D 3L

CONFIDENTIAL

The information contained herein may not be used, disclosed, or published without the written consent of
Biogen Idec MA Inc.

1. INTRODUCTION

Hemophilia A is an X-chromosome-linked bleeding disorder caused by mutations and/or deletions in the factor VIII (FVIII) gene resulting in a deficiency of FVIII activity [Mannucci, 2001; Bolton-Maggs and Pasi, 2003]. The coagulation disorder occurs predominantly in males and affects approximately 1 in 10,000 males. The severity of disease is characterized by the endogenous level of FVIII measured in the plasma. Severe hemophilia A is defined as a level of FVIII coagulant activity (FVIII:C) in plasma of <1% (<1 IU/dL). Individuals with severe hemophilia A experience frequent bleeding and recurrent spontaneous bleeding into the soft tissue and joints, leading to joint damage and severe disability. Repeated bleeding into muscles and joints, which often begins in early childhood, results in hemophilic arthropathy and irreversible joint damage. Damage can lead to limited mobility of joints, muscle atrophy, and chronic pain [Rodriguez-Merchan, 2003].

There is no cure for hemophilia A, so treatment focuses on the replacement of FVIII with the intravenous (IV) administration of FVIII-containing coagulation products to promote clotting. The goal of treatment with FVIII-containing coagulation products is to raise the circulating level of FVIII to the lowest effective level to achieve either resolution of bleeding (on-demand [episodic] treatment) or prevention of bleeding (prophylaxis treatment) [WFH, 2005; MASAC, March 2009]. The frequency of administration of FVIII products varies between patients and is tailored to the patient's clinical status, taking into consideration the type of bleeding episode, frequency of bleeding, and the goal of treatment for the subject. The dose of FVIII required also varies and has been based on observations over the years and guidelines established by organizations such as the National Hemophilia Foundation of the United States and the World Federation of Hemophilia (WFH) [WFH, 2005].

This statistical analysis plan is for the purpose of providing an analysis of long term safety and efficacy data on rFVIII-Fc to support the generation of long-term data on safety, efficacy and other patient reported outcomes. The analysis is based on study 8HA01EXT data only. Study subjects refer only to those subjects enrolled into this study from parent studies 997HA301, 8HA02PED, 997HA307, and 997HA309. A parent study is defined as a study where subjects may be enrolled into 8HA01EXT after study completion.

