16. STATISTICAL METHODS AND DETERMINATION OF SAMPLE SIZE

In general, the data for subjects who enroll from parent studies will be integrated with their data from 8HA01EXT. A parent study is defined as a study where subjects may be enrolled into 8HA01EXT after study completion or at a time specified in the protocol.

All statistical analyses will be descriptive in nature. No formal comparison is planned and no hypothesis will be formally tested. Continuous variables will be summarized and presented by number, mean, median, standard deviation, minimum and maximum, and where appropriate, with the 25th and 75th percentiles. Categorical variables will be summarized by the number and percentage in each category.

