16.6.2. Methods of Analysis

For the analysis of safety, data in 8HA01EXT will be integrated with the parent studies, unless specified otherwise. The incidence of AEs will be tabulated overall, by severity, and by relationship to treatment. In addition, the incidence of AEs will be presented by exposure day (ED) intervals. An ED is a 24-hour period in which one or more rFVIII Fc injections are given. Subject listings will be provided for all AEs, SAEs, AEs resulting in discontinuation of the study treatment or withdrawal from the study, and deaths. Findings in clinical lab values will be summarized by descriptive statistics. Listings of abnormal laboratory test results will be provided.

The total number of EDs of rFVIII Fc will be summarized by treatment regimen and overall for 8HA01EXT, and overall using combined data from the parent studies and 8HA01EXT.

CONFIDENTIAL

The information contained herein may not be used, disclosed, or published without the written consent of Biogen Idec MA Inc.

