16.7.2. Methods of Analysis

The proportion of subjects with inhibitors during rFVIII Fc administration will be provided with the exact (Clopper-Pearson) 2-sided, 95% confidence interval. Any subject with an inhibitor following the initial rFVIII Fc administration will be counted in the numerator; however, only subjects who have completed at least 50 EDs and 100 EDs from their initial rFVIII Fc administration will be included in the denominator. Unless all subjects complete at least 50 EDs, the proportion of subjects with inhibitors will also be calculated using all subjects, regardless of the amount of exposure to rFVIII Fc, in the denominator.

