5.1. General Principles

The following rules will be followed for all applicable analyses contained in this SAP, unless specified otherwise.

Because the subjects from studies 997HA301/997HA307/997HA309 and study 8HA02PED are in different age groups (i.e. ≥ 12 years of age for studies 997HA301/997HA307/997HA309 and < 12 years of age for study 8HA02PED) and may therefore have different safety and efficacy profiles, analyses will be performed separately for the groups of subjects from the parent study or parent studies combined, as described in the table below. Further, the table categories (i.e. age cohort, treatment regimen, etc) by type of analyses for each grouping are also detailed unless specified otherwise.

Groups of subjects from the parent study or parent studies combined	Categories by type of analyses
8HA02PED	Baseline/Concomitant therapy and procedures: Age cohort and overall; treatment regimen (including surgery subgroup) and overall Exposure: Age cohort and overall; treatment regimen and overall Efficacy: Age cohort; treatment regimen Patient-reported outcomes: Age cohort and overall; visit Compliance/surgery/Safety: Visit (if applicable)
997HA301 997HA301/997HA307/997HA309 combined	Baseline/Concomitant therapy and procedures: Treatment regimen (including surgery subgroup) and overall Exposure: Treatment regimen and overall Efficacy: Treatment regimen

	Patient-reported outcomes: Visit Compliance/surgery subgroup/Safety: Visit (if applicable)
Overall	Compliance/Surgery/Safety: Visit (if applicable)

Where treatment regimen (which is defined as treatment regimen in study 8HA01EXT) is:

- Tailored prophylaxis
- Weekly prophylaxis
- Personalized prophylaxis
- Episodic

Age cohort for subjects from study 8HA02PED is as reported for that study, namely:

- <6 years old
- 6 to <12 years old

Summaries of study 8HA01EXT data will be produced using standard summary statistics. Listings will also only include data from study 8HA01EXT and the treatment regimen associated with each data point, unless specified otherwise. Data collected at unscheduled visits will be included in the definition of the maximum and minimum post-baseline values.

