8.2.2. Treatment-emergent Adverse Events

In general, an AE will be regarded as treatment-emergent if it was present prior to receiving the first injection of rFVIIIIFc in the parent study and subsequently worsened in severity, or was not present prior to receiving the first injection but subsequently appeared before the subject's last visit on study or the follow-up phone call, whichever came later (or the date of withdrawal/loss to follow-up).

All AEs that occurred on or after the 8HA01EXT Study Day 1 will be considered treatment-emergent in study 8HA01EXT, regardless of the gap between the parent study and study 8HA01EXT. AEs that were treatment-emergent in the parent studies and carried over to study 8HA01EXT without worsening in severity will be considered the same AEs and will not be counted again in study 8HA01EXT.

The incidence of TEAEs will be summarized by system organ class (SOC) and preferred term. Unless specified otherwise, SOCs and preferred terms within each SOC will be presented alphabetically. For the purpose of summarization, a subject is counted once in a SOC or preferred term if the subject reported one or more events in that SOC or preferred term. Unless specified otherwise, percentages will be based on the number of subjects in the Safety Analysis Set.

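### The SAP confines safety and exposure analyses to 8HA01EXT data and plans no cumulative exposure-day or AE summary from the first rFVIIIFc dose, although the protocol calls for combined data

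*SAP*

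**What the plan says.** **Protocol.** Section 16 sets a general rule: "In general, the data for subjects who enroll from parent studies will be integrated with their data from 8HA01EXT". Section 16.6.2 applies it to safety, with an exception clause: "For the analysis of safety, data in 8HA01EXT will be integrated with the parent studies, unless specified otherwise". The same section asks for total rFVIIIFc EDs by regimen and overall within 8HA01EXT, and then "overall using combined data from the parent studies and 8HA01EXT". That last request has no exception clause.

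**SAP.** Section 5 says the plan is based on protocol Version 3. Section 1 nevertheless states: "The analysis is based on study 8HA01EXT data only". The rest of the SAP follows that scope:
- Section 5.1 bases summaries on 8HA01EXT and adds: "Listings will also only include data from study 8HA01EXT", unless specified otherwise.
- Section 5.3.4 starts the safety period at 8HA01EXT Study Day 1.
- Section 7.3.2 counts EDs, injections and duration of dosing only between the first and last treatment regimen in 8HA01EXT.
- Section 8.2.2 says that parent-study TEAEs carried over without worsening "will be considered the same AEs and will not be counted again in study 8HA01EXT".
- The list of tables contains no integrated AE, SAE or exposure table.

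**The concern.** The primary objective is the long-term safety of rFVIIIFc, and subjects enter the extension already exposed. Extension-only tables start after the parent-study treatment period. In 997HA301, 146 of 164 subjects had been treated for at least 26 weeks, and 8HA02PED plans at least 26 weeks (protocol 5.1.3). A reader of the final report would not find each subject's AE experience or total exposure from the first dose, which is what integration was meant to supply.

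Two other parts of the SAP presuppose a cumulative view that no output delivers. Section 3.1 sets the 100-ED target for children across parent and extension study together. Section 8.2.2 anchors its general definition of treatment emergence to the first injection in the parent study.

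**Working it through.** **1. Commitment against planned output**

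| Item | Protocol | SAP |
|---|---|---|
| Cumulative EDs, parent plus extension | Required in 16.6.2, no qualifier | No output; 7.3.2 counts within 8HA01EXT |
| AE and SAE data scope | Integrated by default (16, 16.6.2), exceptions allowed | Extension only; no reason given |
| AEs by exposure | 16.6.2: "the incidence of AEs will be presented by exposure day (ED) intervals" | No such table |
| ED count for inhibitor denominators | 16.7.2: "only subjects who have completed at least 50 EDs and 100 EDs from their initial" rFVIIIFc administration | No cumulative ED count planned |

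The first row is a firm commitment that the SAP does not meet. The second is an unexplained departure from a default. The last two rows are separate gaps, shown here because an ED count from first dose is also relevant to them.

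**2. Subject numbers reproduced**

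Protocol 16.10: 144 + 50 = 194. SAP 3.3.1: 144 + 50 + 12 + 8 = 214. Both agree with the stated totals.

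**3. A child at the 100-ED target**

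8HA02PED plans at least 50 EDs. With 50 parent EDs and 50 extension EDs, the total is 50 + 50 = 100, so the target in SAP 3.1 is met. SAP 7.3.2 counts only the 50 extension EDs and places him in the 50 to <100 category.

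**4. Parent-study time left out**

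Inputs from protocol 5.1.3: 102.05 person-years in 164 treated subjects of 997HA301, and about 50 children in 8HA02PED planned for at least 26 weeks.
- 8HA02PED: 50 × 26 / 52.18 = 24.9 person-years (planned minimum).
- Upper figure, with all 997HA301 time counted: 102.05 + 24.9 = about 127.
- Scaled figure, with 997HA301 time reduced to the 144 subjects in the sample-size basis: 102.05 × 144 / 164 = 89.6, and 89.6 + 24.9 = about 115.

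Share of cumulative time = P / (P + 214 × f), where P is parent-study time and f is mean extension follow-up in years. The documents give only a maximum of 4 years, so f is assumed.

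| f (years) | Extension time | Share, P = 127 | Share, P = 115 |
|---|---|---|---|
| 1 | 214 | 37% | 35% |
| 2 | 428 | 23% | 21% |
| 4 | 856 | 13% | 12% |

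Parent-study time in 997HA307 and 997HA309 is not given and is not included.

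**5. Carried-over AEs**

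An extension-only TEAE table counts events that start or worsen in 8HA01EXT. A parent-study TEAE that continues unchanged is excluded by SAP 8.2.2, and no integrated table exists in which it would be counted once. Its TEAE incidence count under this SAP is zero.

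**The case against.** The strongest reply concerns AEs. Protocol 16 states its rule only as a general one, and 16.6.2 lets exceptions be specified. The SAP does specify otherwise, openly and consistently, and extension-only AE tables are a defensible choice. This stands: the AE scope is an unexplained departure from a default, not a breach of a fixed rule. It does not cover the combined ED summary, which has no exception clause.

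A reader might also infer more than the documents support:
- *That carried-over AEs disappear.* Only those that did not worsen are excluded from TEAE counts. SAP 8.2 lists all AEs, so unworsened events may appear there. The overall summary in 8.2.1 has rows for discontinuation due to an AE and for death that are not limited to TEAEs.
- *That the early safety data go unreported anywhere.* This SAP governs one study's final report. The parent-study reports are not available here, and the wording in 8.2.2 implies those events were counted there.
- *That no parent-study data are used.* Race and ethnicity (6.2.1), the target-joint subgroup (7.3.1) and baselines taken at the parent end-of-treatment visit (5.1) all come from the parent studies.
- *That the lost time can be turned into an upper bound on an event rate per subject-year.* SAP 8.2 defines AE incidence as a proportion of subjects in the Safety Analysis Set, so such a bound matches no planned statistic.
- *That children generally lose half their exposure.* That holds only for a child who stops at exactly 100 EDs. With an assumed two doses a week for 4 years, extension EDs are 2 × 52 × 4 = 416, and 50 parent EDs are 50 / 466 = about 11%.

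Finally, integration has its own bias. Entry requires completion of a parent study (protocol 8.1). Parent-study time in enrolled subjects therefore leaves out those who stopped early, perhaps including the 997HA301 subject who discontinued for rash. This is a reason to label integrated tables carefully, not to omit the ED summary.

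**Conclusion.** The point holds in this form: the SAP omits a cumulative-ED summary that the protocol requires without qualification, and it drops the protocol's default integration of AE data without saying why. Unworsened carried-over TEAEs consequently enter no TEAE incidence count.

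The parent-study time left out is about 115 to 127 person-years, or roughly 12% to 37% of the cumulative total. This rests on an assumed mean extension follow-up of 4 years down to 1 year, on all 214 eligible subjects enrolling, on the planned minimum for 8HA02PED, and on reading the protocol's 102.05 person-years on study as a proxy for treatment time. The textual finding depends on none of these figures. The SAP should be changed. The point bears on the completeness of the long-term safety account; it does not show that any planned table is wrong for the extension period it covers.

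**What to change.** - **SAP 7.3.2 and the list of tables:** add an overall summary of cumulative EDs and duration of dosing from the first rFVIIIFc dose in the parent study. This alone meets the unqualified protocol commitment.
- **SAP 1, 4.3 and 8:** define an integrated parent-plus-extension safety data set for subjects enrolled in 8HA01EXT. From it, produce the overall TEAE summary and the TEAE and SAE tables by system organ class and preferred term. Keep the 8HA01EXT-only tables beside them.
- **SAP 8.2.2:** align the definition of treatment emergence with each data scope, and count every unworsened carried-over AE once, in the integrated table.
- **Any AE table left extension-only:** state the departure from protocol 16.6.2 and the reason for it.
- **Footnote on integrated tables:** say that parent-study time in enrolled subjects is conditional on completing the parent study, so early AEs may be understated.

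The cost is SAP text, a modest number of additional tables, and some alignment of coding and visit conventions across studies. The SAP already uses parent-study dose and visit dates to set Study Day 1 (5.1.1). It also plans a listing of AEs that began before Study Day 1 and were not reported in the parent study, so some linkage to parent-study records is needed already.
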